Fasting cortisol (nmol/L)			+			+		+
Fasting ACTH (pmol/L)			+			+		+
Fasting copeptin (pmol/L)			+			+		+
Fasting Lipids/lipoproteins ^e (mmol/L)/(g/L)			+			+		+
C-reactive protein (mg/L)			+			+		+
Creatinine (µmol/L)	+		+	+	+	+	+	+
eGFR (mL/min/1,73 m ²)	+		+			+		+
Sodium (mmol/L)	+		+	+	+	+	+	+
Potassium (mmol/L)			+	+	+	+	+	+
Urea (mmol/L)			+	+	+	+	+	+
Osmolality (mOsm/kg)			+	+	+	+	+	+
Erythrocyte Volume Fraction (%)			+					+
HbA1c (mmol/mol)			+					+
Plasma samples for long term storage			+			+		+
Whole blood for DNA isolation			+					
URINE								
24-hour urine sample		+		+	+	+	+	+
Urine volume (ml)		+		+	+	+	+	+
Creatinine (mmol/24h)		+		+	+	+	+	+
Sodium (mmol/24h)		+		+	+	+	+	+
Potassium (mmol/24h)		+		+	+	+	+	+
Urea (mmol/24h)		+		+	+	+	+	+
Osmolality (mOsm/kg)		+		+	+	+	+	+
Albumin/creatinine ratio (g/mol)		+				+		+
Cortisol (nmol/24h)		+				+		+

Urine for long term storage		+				+		+
FAECES								
Sample for microbiome seq			+					+
Bristol stool score			+					+
Check for adverse events				+	+	+	+	+
^a Pre-randomization. ^b Time after randomization. ^c Clinic visits 8 time points: visit 1, visit 2, baseline, 3 weeks & 3, 6, 9 and 12 months after baseline. ^d In addition to coaching during telephone contacts and by a Bluetooth water bottle. ^e triglycerides, LDL, HDL, ApoA1, ApoB.								

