The signature of the study informed consent form marks the inclusion of the subject in the study. This signature will be obtained after having fully briefed the subject about the study and answered all of his/her questions about the study.

Safety reporting: The following variables will be followed at each visit in order to assess safety measurements: serum creatine, serum osmolality and serum sodium to control for water balance problem.

Definition and registration of adverse events: An adverse event (AE) is defined as any untoward medical occurrence in a participant who is administered an investigational product. The medical occurrence does not necessarily have to have a causal relationship with the treatment. An AE can therefore be any unfavorable and unintended sign (including an abnormal laboratory finding, symptom, or disease temporally associated with the use of an investigational product, whether or not related to the investigational product.

AEs are defined as either a laboratory measurement outside the reference range (i.e. a value outside the reference values) or signs or symptoms reported by the participants during regular follow-up contacts (telephone calls and visits). During these contacts the participants will be asked if it has occurred any new or worsened health problems or any medical treatment or hospitalization since the last contact. AEs are documented in the eCRF. We will specifically ask about pregnancy, lactation and new use or change of medication.

AEs are categorized as serious (SAEs) if they result in death, illness requiring hospitalization, events deemed life-threatening, or if they result in persistent or significant disability/incapacity, or in a congenital anomaly/birth defect or medically important condition. SAEs will be reported to the sponsor within 24 hours, as well as recorded in the eCRF (V-CMS). The sponsor will report all SAEs to Danone Research within 3 days. The Adverse Event Form will be sent by email/fax to the following contact:

Position(*)	Name	Cell Phone	Email
Clinical Operations Leader	[name]	[contact]	[contact]
Hydration Physiology and Metabolism Junior Scientist	[name]	[contact]	[contact]

Registration of AEs will start with the 1st telephone contact (which is the first follow up after start of treatment). The registration of AEs ends at the 12-month visit (end of treatment).

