### 5.1.3 Populations

We expect a final study sample for intention to treat analysis of at least n=544 evaluable study subjects who have completed the protocol (i.e. with at least 2 fasting glucose measurements, meaning at V3 and at either V6 or V8 or at both V6 and V8). We expect a dysbalance in the final study sample (46% intervention vs 54% control therapy) due to dysbalance in the drop-out rate between intervention and control groups.

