## Analysis of safety

### 5.7.3 Adverse events

See section “*Definition and registration of adverse events*” of the protocol. AE and SAE will be reported for all subjects who attended baseline exam and commenced study treatment (i.e. attended V3). AE and SAE will be reported as a diagnosis code (<http://icd.internetmedicin.se/>) associated with the AE/SAE, and the incidence of AE and SAE will be compared between treatment groups (intervention vs control).

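### Laboratory adverse events are counted whatever the baseline value and pooled with reported events, so the comparison between arms is diluted and, with unequal dropout, can flatter the water arm

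*Protocol*

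**What the plan says.** The protocol (Definition and registration of adverse events) gives a general definition under which "The medical occurrence does not necessarily have to have a causal relationship with the treatment". It then makes it operational: "AEs are defined as either a laboratory measurement outside the reference range (i.e. a value outside the reference values) or signs or symptoms" reported at contacts. The only new-or-worsened condition is in the question put to people: "participants will be asked if it has occurred any new or worsened health problems or any medical treatment or hospitalization since the last contact". It does not apply to laboratory values. "Registration of AEs will start with the 1st telephone contact (which is the first follow up after start of treatment"), so a value already abnormal at V3 first counts when it is abnormal again in follow-up.

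SAP 5.7.3 refers back to this definition, takes everyone who attended V3, reports events by diagnosis code, and says that "the incidence of AE and SAE will be compared between treatment groups (intervention vs control"). SAP 4.1 (Intention to treat) instead places AE and SAE evaluation in the set with at least two fasting glucose values. On retention, SAP 5.1.3 says: "We expect a dysbalance in the final study sample (46% intervention vs 54% control therapy"). SAP 6.3 describes dropout as balanced between V2 and V3 and slightly unbalanced afterwards.

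**The concern.** Three features combine.

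- **No baseline condition.** Type 2 diabetes not treated with insulin is allowed (the protocol expects about 4–6%), only eGFR below 30 is excluded, and SAP 5.5 anticipates lipid-lowering and antidiabetic drugs at V3. Out-of-range glucose, HbA1c, lipids or creatinine will be present in some participants before treatment starts, and can then be counted as events.
- **Uneven testing.** Far more analytes are tested at 6 and 12 months than at the other follow-up visits, so laboratory events cluster there whatever the treatment does.
- **Pooling.** Nothing separates these flags from symptoms and diagnoses. A real difference in reported events can be lost among background flags. If fewer water-arm participants reach the large-panel visits, they also have fewer chances to be flagged.

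At stake is whether the AE table can show a difference between arms, and whether an apparent safety advantage for water could arise from attendance.

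**Working it through.** The documents give no AE rate, so there is no stated figure to reproduce. Out-of-range rates, correlations, absolute retention and the true AE difference below are assumptions.

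**1. Tests per visit (Protocol, Table 1).**
- 3 weeks, 3 and 9 months: creatinine, sodium, potassium, urea, osmolality = 5.
- 6 months: these plus eGFR, glucose, insulin, glucagon, cortisol, ACTH, copeptin, five lipids/lipoproteins and CRP = 5 + 13 = 18.
- 12 months: plus erythrocyte volume fraction and HbA1c = 20.
- Other counting rules give 17 and 19 (without copeptin, which is batched after the trial) or 21 and 23 (2-hour glucose, insulin and glucagon counted separately).
- Total 5 + 5 + 18 + 5 + 20 = 53, of which 38 (72%) fall at 6 and 12 months.
- Urine adds six measures at every follow-up visit and eight at 6 and 12 months. The visit counts become 11, 11, 26, 11 and 28, total 87, and the 6- and 12-month share is 54/87 = 62%.

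**2. Chance of at least one blood flag with no treatment effect.** For m independent tests with out-of-range rate q, P = 1 − (1 − q)^m.

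| q | 5 tests | 18 tests | 20 tests | 53 tests |
|---|---|---|---|---|
| 1% | 5% | 17% | 18% | 41% |
| 5% | 23% | 60% | 64% | 93% |

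Tests within a person are correlated. A one-factor threshold model averages 1 − (1 − q(z))^m over a standard normal z, where q(z) = Φ((√ρ·z − t)/√(1 − ρ)) and t = Φ⁻¹(1 − q). With q = 5% and ρ = 0.5 the row becomes 17%, 33%, 34% and 48%. With q = 1% and ρ = 0.5 the 53-test figure is 18%.

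**3. Dilution with equal follow-up.** Assume a true AE difference of 12% against 5%, with 544 × 0.46 ≈ 250 and 544 × 0.54 ≈ 294 participants. If a share B of both arms also has a background laboratory AE, incidence becomes 1 − (1 − p)(1 − B). At B = 30% this gives 1 − 0.88 × 0.70 = 38.4% against 1 − 0.95 × 0.70 = 33.5%. Power (two-sided 5%, normal approximation) is 84% at B = 0, 22% at 30%, 13% at 50% and 5% at 90%.

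**4. Unequal dropout, all V3 attenders as denominator.** Assume control retention of 90%. With 1:1 allocation and balanced loss before V3, a 46:54 split implies water retention of 0.90 × 46/54 = 76.7%. Assume leavers are seen only at 3 weeks and 3 months (10 blood tests). The gap with no treatment effect is (0.90 − 0.767) × (F − E), where F and E are the chances of any flag over 53 and 10 tests.
- q = 5%, independent: 0.133 × (0.934 − 0.401) = 7.1 points.
- q = 5%, ρ = 0.3: 4.5 points; ρ = 0.5: 3.1 points.
- q = 1%, independent: 0.133 × (0.413 − 0.096) = 4.2 points; ρ = 0.5: 1.5 points.

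A second model lets each analyte correlate 0.5–0.7 across visits and analytes correlate 0–0.3 with each other. At q = 1–5%, 27–89% of full attenders and 8–37% of early leavers have a flag, and the gap at the same retention is about 2.5 to 7 points.

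**5. What a baseline rule alone removes.** In that second model, 13–39% of follow-up flags were already out of range at V3, so 61–87% would remain.

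**6. What the five every-visit analytes alone achieve.** A full attender has 25 such tests and an early leaver 10. At q = 5%, independent, the gap is 0.133 × (0.723 − 0.401) = 4.3 points instead of 7.1. At q = 1% it is 0.133 × (0.222 − 0.096) = 1.7 instead of 4.2. Restricting the analytes reduces the artefact but does not remove it.

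**The case against.** A reader might infer that AE incidence tracks the test schedule instead of water, that the comparison sits near a ceiling, or that it cannot show new abnormalities caused by water. The documents do not support these readings.

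- Both arms share one schedule under 1:1 randomization. With equal attendance, extra flags arise in both arms and dilute a difference; they do not create one.
- Sodium, osmolality and creatinine, the variables the protocol names for monitoring water balance, are measured at every visit. The step in panel size does not touch them.
- Reported symptoms do not depend on the panel, and SAEs have their own criteria.
- Most of the added analytes are also analysed as baseline-adjusted change by arm (SAP 5.7.2), where a water effect on them could be seen.
- The near-ceiling figures need a 5% out-of-range rate and nearly independent analytes. Yet eGFR is derived from other data, and pairs such as LDL with ApoB or glucose with HbA1c clearly move together.
- The dropout bias depends on the analysis set. In the SAP 4.1 set everyone has reached V6 or V8, so early leavers are absent.
- Read literally, the definition also covers urine, where the arms are meant to differ. Part of the laboratory AE count could then follow water directly.

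All of this stands and limits the claim. Two possible defences do not settle it. Diagnosis coding might drop isolated laboratory values, but no rule says so. The nurse's check of out-of-reference results (Protocol, Data handling) is data validation, not an AE filter.

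**Conclusion.** The point holds in a limited form. The protocol states a rule under which pre-existing laboratory abnormalities become events, and SAP 5.7.3 carries them into one pooled incidence comparison. The main consequence is dilution: under the assumed 12% against 5%, power falls from 84% to 22% once 30% of both arms carry a background flag. The secondary consequence is a spurious advantage for water of roughly 2 to 7 points. It rests on assumed out-of-range rates of 1–5%, assumed retention of 90% against 77%, leavers seen only at 3 weeks and 3 months, and all V3 attenders as denominator. Seven points is the upper end, and strong correlation with a low rate gives about 1.5. In the set with at least two fasting glucose values this bias largely disappears, at the price of losing early leavers' events. Because the SAP names both sets, the size of the bias cannot be fixed until that conflict is resolved.

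**What to change.** Amend SAP 5.7.3. These changes concern the comparison between arms only; what is recorded and followed up in individuals is unaffected.

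1. Count a laboratory AE in the comparison only if the value was in range at baseline (V3, or V2 for urine) and out of range later, or clearly worse than at baseline by a rule set in advance.
2. Tabulate laboratory AEs separately from participant-reported AEs and SAEs, and make no pooled comparison.
3. For the whole-period laboratory comparison use the five blood analytes measured at every visit, and give the number of tests or visits contributed per arm, since dropout still shortens exposure. Show analytes measured only at 6 and 12 months by visit with the number tested per arm, and note that this conditions on attendance.
4. Treat the intended changes in urine volume and osmolality as adherence measures, not AEs, in this comparison.
5. Reconcile the AE analysis set between SAP 4.1 and SAP 5.7.3.

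The cost is wording and a few extra tables; Table 1 already schedules the baseline values. The headline AE count will fall, and fluctuation around reference limits will still produce some treatment-emergent flags. Item 2 therefore matters most.

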## 1 Abbreviations and definitions

### Acronyms

ACTH: Adrenocorticotrophic Hormone

AE: Adverse Event

OGTT: Oral Glucose Tolerance Test

RCT: Randomized Control Trial

SAE: Serious Adverse Event

VP: Vasopressin

V3: Visit 3, baseline visit

V6: Visit 6

V8: Visit 8

## 2 Introduction

The study is a single-centre parallel group randomized clinical trial comparing the effect of a water intake supplementation intervention vs. a control group in subjects with a high plasma level of vasopressin (VP) (measured by a stable VP marker of its precursor hormone called “copeptin”) on fasting levels of glucose (primary outcome measure), risk of new-onset diabetes and other cardiometabolic risk factors (secondary outcome measures).

The intervention group will increase its daily water intake by 1,5L on top of habitual water intake. The control group will not change its daily water intake.

No interim analyses are planned. The final analysis is performed at the end of the study using the final database lock (randomized and complete subjects are currently planned).

This Statistical Analysis Plan (SAP) describes the planned statistical analyses including methods used, derivations and outputs to be provided.

## 3 Description of the study

### 3.1 Study objectives

To study if water supplementation in subjects with high plasma levels of VP (measured by copeptin) can reduce fasting levels of glucose, risk of new-onset diabetes and other cardiometabolic risk factors in comparison with subjects with high VP who do not change their water intake.

### 3.1.1 Primary objectives

To assess if water supplementation during one year reduces fasting plasma glucose levels.

### 3.1.2 Secondary objectives

To assess if the water supplementation during one year alters

- the diabetes incidence

- the level of cardiometabolic risk factors (2-hour glucose during oral glucose tolerance test (OGTT), HbA1c, waist circumference, body mass index, systolic and diastolic blood pressure, serum triglycerides, HDL- and LDL cholesterol, Apo-B, Apo-A1, cortisol, Adrenocorticotrophic hormone (ACTH), insulin (fasting and 2h post OGTT), C-reactive protein, estimated GFR, Creatinine clearance) and plasma concentration of copeptin.

### 3.1.3 Exploratory objectives.

Exploratory objectives are not part of primary or secondary outcomes and the exact analyses methods are not detailed here. To assess if water supplementation during one year leads to alterations in

- Reported diet intake. This objective is exploratory but reported diet intake regarding alterations in e.g. sugar sweetened beverages and adherence to Nordic Diet Recommendations 2023 can have an important mediating effect on both primary and secondary endpoints. Reported diet intake was collected using a software from the Swedish National Food Agency, and they declined continuation of the license from last quarter of 2023. Thus, we have missing data in subjects who had not completed their V8 before that time point. We estimate approximately 30% of missing data for the diet analyses (i.e. do not have complete data at baseline and V8). We plan exploratory analyses to test if water vs control therapy leads to differences in change of intake of main nutrients (protein, carbohydrates and fat energy intake relative to total caloric intake) over the 12-month period. These analyses will be performed using t-test (treatment group differences between delta values).

The first step of statistical analysis will be to produce descriptive statistics for some baseline parameters on reduced population (those with baseline and at least one post-baseline value), by intervention group and compare those results with the ITT population. Variables taken into account are those potentially impacting the primary outcome (fasting glycemia) and could be the sex (Male/Female), the age at enrolment (Years), the BMI at baseline ( $\text{kg}/\text{m}^2$ ), the total energy intake at baseline ( $\text{kcal}/\text{day}$ ) from three non-consecutive days of 24-h dietary recall, if possible, 2-h plasma glucose level from OGTT at baseline ( $\text{mmol}/\text{L}$ ) and the waist circumference (cm). If we notice a clinical imbalance between study groups (control and intervention groups in the reduced population vs. the ITT population) for those variables, they could be considered as potential covariates in sensitivity models for primary and secondary analysis. Three other variables could also be considered for the sensitivity analysis: newly diagnosed with T2DM (Yes/No), management of T2DM (initiation of intensive lifestyle therapy if possible and initiation of hypoglycemic drug therapy) and drug therapy impacting the fasting glycemia (Yes/No).

The second step will be driven by both previous results (the real number of missing data and potentially imbalanced covariates detected in the previous step). The idea is to perform sensitivity analyses for primary and secondary endpoints with dietary records (minimum baseline and one post-baseline value; maximum 3 data points per subject) including covariates that tend to cause imbalance between the intervention study groups.

- Gut microbiome composition. This is a second exploratory objective. Currently, we have only saved stool samples in the biobank, but since we do not yet have funding for microbiome profiling, it is unclear which method will be used (level of resolution i.e. 16S vs metagenomic shotgun sequencing) will require completely different statistics and bioinformatics. Thus it is not possible at this stage to provide a statistical analysis plan for this potential exposure. If any impacts of water treatment on primary or secondary outcomes are observed, and if funding allows measurement, a SAP - adjusted to the method of choice - will be written at a later stage.
- Plasma metabolome: Also for this third exploratory objective, funding is not currently available and range methodological resolution and cost is wide. Thus, like described for the microbiome, if funding allows measurement, a SAP- adjusted to the method of choice - will be written at a later stage.

[figure not shown]

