Assessment of outcome and baseline characteristics (TABLE 1): Clinic visits are performed at baseline, 3 weeks, 3, 6, 9 and 12 months at which cardiometabolic risk factors and hydration parameters are measured as detailed in **TABLE 1**. Please note that the main outcome variables are measured at baseline, 6 months and 12 months. The purpose of the other clinic visits is to optimize adherence to the allocated treatment arm. All laboratory analyses will be performed using certified methods. In addition, we will record medication, fluid/water and dietary intake and medical history. The gut microbiota composition has been suggested to mediate systemic metabolic changes. As stool consistency, in turn highly affected by water intake, has been shown to be one of the main factors determining the microbiota composition (Science 2016;352:560-4), we will measure the gut microbiota in order to test if such changes may mediate part of any beneficial effects of water supplementation on metabolism. Stool consistency will be assessed using a Bristol score chart. Furthermore, as recent work shows that genetic factors play a role in determining basal level of VP (measured by copeptin) (J Clin Endocrinol Metab 2016;101:2432-9), it can be hypothesized that the magnitude of the copeptin lowering effect by water – and the potential effects of metabolism – varies according to such genetic factors. Therefore, we will also isolate DNA from buffy coats in order to determine such genetic variation.

TABLE 1. Schedule of visits and measures

				Follow-up^{b,c}				
	Visit 1 <small>a,c</small>	Visit (Inclusion) <small>a,c</small>	Baseline (Week 0)	3 weeks	3 months	6 months	9 months	12 months
				+/- 4 days	+/- 14 days	+/- 14 days	+/- 14 days	+/- 14 days
Informed Consent Process and Informed Consent Form Signature	+							
Exclusion criteria check-up including pregnancy	+							
Randomization			+					
SURVEY								
Demographics			+					

Diet (4-day report)			+			+		+
Health history			+			+		+
Health-related quality of life			+			+		+
Hydration coaching ^d			+	+	+	+	+	
CLINICAL								
Height (cm)			+			+		+
Weight (Kg)			+			+		+
Waist circumference (cm)			+			+		+
Blood pressure (mm Hg)			+			+		+
Medications			+			+		+
BLOOD								
Blood sample	+		+	+	+	+	+	+
Fasting glucose (mmol/L)			+			+		+
Oral glucose tolerance test (OGTT) (mmol/L)			+			+		+
Fasting and 2h insulin (during OGTT) (mIE/L)			+			+		+
Fasting and 2h glucagon during OGTT) (pmol/L)			+			+		+

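### The diet comparison in SAP section 3.1.3 uses an unadjusted t-test of change scores; adjusting for baseline diet and sex would be more precise and needs no new data

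*SAP*

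**What the plan says.** Section 3.1.3 of the SAP opens by limiting its own scope: "Exploratory objectives are not part of primary or secondary outcomes and the exact analyses methods are not detailed here". It then does name an analysis for diet. The arms are to be tested for "differences in change of intake of main nutrients" (protein, carbohydrate and fat as shares of total energy) over 12 months, and "These analyses will be performed using t-test (treatment group differences between delta values". No baseline, sex or visit term is mentioned, and no analysis set is given for this test.

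The dietary software licence ended in the last quarter of 2023. The SAP says: "Thus, we have missing data in subjects who had not completed their V8 before that time point". It adds: "We estimate approximately 30% of missing data for the diet analyses (i.e. do not have complete data at baseline and V8".

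Table 1 of the protocol schedules the diet record ("Diet (4-day report") at baseline, 6 months and 12 months. Section 3.1.3 uses the 6-month records in a different analysis: "The idea is to perform sensitivity analyses for primary and secondary endpoints with dietary records", with "minimum baseline and one post-baseline value; maximum 3 data points per subject". The reduced population described earlier in that section is likewise baseline plus at least one later value.

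Elsewhere the SAP adjusts. Section 4.1 (Missing data) adjusts outcome analyses for the baseline value of the outcome, citing regression towards the mean, and for sex, the stratification factor. Section 5.6.2 puts both into a mixed model of 6- and 12-month glucose change. Section 5.7.2 applies the same method to the cardiometabolic risk factors.

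**The concern.** A difference of raw change scores carries the noise of both the baseline and the follow-up record. A few days of recorded intake is a short sample of habitual diet, so the correlation between two such records may be only moderate. That is where a change score wastes most information compared with adjusting for baseline. The trial already holds the baseline value, and the SAP already has a model that uses it.

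The precision is worth having. Section 3.1.3 says that diet may mediate effects on the primary and secondary endpoints, and about 30% of subjects are expected to lack a complete baseline and V8 pair. A wider confidence interval makes a real diet difference between arms easier to miss.

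**Working it through.** **Inputs from the documents**
- About 30% without complete baseline and V8 diet data, so about 70% complete (SAP 3.1.3). No diet counts by visit are given, so this figure cannot be recomputed.
- 544 evaluable subjects (SAP 3.3), split 46% intervention and 54% control (SAP 5.1.3). The denominator of the 30% is not stated; 544 is taken here as an assumption.

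**Check of the denominator.** With difference 0.14, SD 0.58, two-sided 5% and 80% power, n per group = 2 × (1.960 + 0.842)² × 0.58² / 0.14² = 269.4, so 270, as stated. With a 46:54 split the need is 250 + 293 = 543, against the stated 544.

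**Assumptions**
- r, the correlation between baseline and 12-month diet values, is not in the documents. The range 0.4 to 0.7 is used.
- The variance σ² is the same at both visits.

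**Variance of the arm difference.** Both methods share the factor (1/n₁ + 1/n₂), so only the per-subject variance matters:
- change score: 2σ²(1 − r)
- baseline-adjusted: σ²(1 − r²)
- ratio: (1 − r²) / [2(1 − r)] = (1 + r)/2

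If the variances differ (σ₀ at baseline, σ₁ at 12 months), the change-score variance exceeds the adjusted one by (σ₀ − rσ₁)². This is never negative, so in a large sample adjustment cannot lose precision.

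**Size.** Complete pairs: 0.70 × 544 = 380.8, about 381 (175 intervention, 206 control).

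| r | variance ratio | extra subjects the t-test needs | t-test N matching an adjusted analysis of 381 |
|---|---|---|---|
| 0.4 | 0.70 | 1/0.70 − 1 = 43% | 544 |
| 0.5 | 0.75 | 33% | 508 |
| 0.6 | 0.80 | 25% | 476 |
| 0.7 | 0.85 | 18% | 448 |

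**Detectable difference** at 80% power and two-sided 5% (the SAP states no level for diet). For the t-test on 381 it is 2.802 × √(1/175.2 + 1/205.6) = 0.288 SD of the change. On all 544 it would be 0.241 SD. With baseline adjustment on 381 it is 0.288 × √((1 + r)/2), which gives 0.241 at r = 0.4 and 0.266 at r = 0.7. So at r = 0.4 adjustment recovers what the missing 30% cost the t-test.

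**What V6-only subjects add.** Assume one common correlation r between all visits, and that the 70% with complete pairs also have V6. Given baseline, the residual correlation between the 6- and 12-month values is (r − r²)/(1 − r²) = r/(1 + r). If a further share f has V6 but no V8, the variance of the 12-month contrast falls by [r/(1 + r)]² × f/(0.70 + f).
- r = 0.3, f = 0.05: 0.0533 × 0.0667 = 0.4%
- r = 0.5, f = 0.10: 0.1111 × 0.125 = 1.4%
- r = 0.7, f = 0.20: 0.1696 × 0.222 = 3.8%

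The gain therefore comes almost entirely from the baseline term.

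**The case against.** The strongest defence is that nothing is broken. The objective is exploratory and the SAP says its methods are not fully specified. The baseline rule in section 4.1 is framed around glucose change and the secondary cardiometabolic measures, so the t-test contradicts no rule that clearly covers diet. A t-test of change is a valid randomized comparison when missingness is unrelated to outcome, and a licence ending on a calendar date plausibly is. Regression towards the mean acts in both arms and does not bias the contrast. All of this stands. It makes the point one of precision and keeps the severity low, but it does not supply a reason to prefer the less precise test.

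Three stronger readings might be inferred and are not supported.

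- *The V6 diet records are thrown away, and most of the missing 30% could be recovered from them.* Section 3.1.3 uses V6 records in the sensitivity analyses of the primary and secondary endpoints. That the t-test uses only baseline and V8 is itself an inference from the 12-month period and the definition of missing data. The 30% counts subjects without a complete baseline and V8 pair, which can include dropouts and people with no baseline record. No figure says how many have V6. With V6 and V8 six months apart, V6-only cases caused by the lapse come from roughly a six-month enrolment window.
- *Diet is the only continuous variable treated this way.* Section 5.4 lists paired tests for urine measures, and section 5.7.1 lists copeptin and albumin/creatinine ratio under headings separate from the cardiometabolic risk factors.
- *A null diet result will be used to rule out diet as an explanation.* The SAP does not say so. Its examples of mediating diet changes are sweetened drinks and adherence to Nordic recommendations, not the macronutrient shares tested here.

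**Conclusion.** The point holds as a low-severity loss of precision. The planned t-test leaves out a baseline value that the trial collects and the sex term that the SAP uses elsewhere. Under equal visit variances and an assumed r of 0.4 to 0.7, baseline adjustment would cut the variance of the arm difference by 15% to 30%. The direction of the gain does not depend on those assumptions; its size does. The gain from sex is not quantified here.

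It is not a finding of bias. The one caution is ordinary dropout, which section 5.1.3 expects to differ by arm. For those losses, independence from outcome is less clear than for the licence lapse.

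**What to change.** Replace the t-test sentence in section 3.1.3 with a model of diet change adjusted for baseline diet value and sex. The simplest choice is the section 5.6.2 mixed model: change at V6 and V8, with baseline value of the diet variable, sex, treatment, visit and treatment-by-visit interaction, reporting the 12-month contrast with its 95% confidence interval. State the analysis set as subjects with baseline and at least one later diet record, which is the reduced population that the section already describes. The direct diet comparison and the diet sensitivity analyses would then rest on the same population rule.

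The cost is one or two sentences in the SAP and reuse of the planned PROC MIXED code, with no new data or visits. The change should be made before diet data are examined by arm. If the t-test is kept for simplicity, a single-visit regression of 12-month change on arm, baseline value and sex would capture nearly all of the gain.
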